Cases are defined as participants meeting clinical criteria based both on symptoms for COVID-19 and on RT-PCR detection of SARS-CoV-2 from samples collected within 72 hours of the study participant reporting symptoms meeting the definition of COVID-19. Participants who are hospitalized for COVID-19 without the opportunity for a clinic visit will also be considered cases, assuming that the symptomatology criteria for COVID-19 are met and a respiratory sample is positive for SARS-CoV-2 by PCR at a Clinical Laboratory Improvement Amendments (CLIA)-certified or CLIA-certified waiver laboratory. Investigators are encouraged to try to obtain a respiratory sample during the course of hospitalization for submission to the study central laboratory, if feasible.

Symptomatic COVID-19 is defined by the presence of one of the CDC-listed symptoms ([CDC 2020](#)) and a positive RT-PCR test on a respiratory sample. Asymptomatic SARS-CoV-2 infection is defined as a positive RT-PCR test on a respiratory sample in the absence of symptoms or a positive serologic test for antinucleocapsid antibody after a negative test result at the time of enrollment, with the serologic assay detecting previously resolved SARS-CoV-2 infections that may have occurred between visits, and the RT-PCR to detect active viral infection at the time of a visit. If participants are confirmed to have SARS-CoV-2 infection and are symptomatic or asymptomatic, the investigator will notify the participants' primary care physicians of the diagnosis and the local public health authorities as required per local regulations.

If the participant had known exposure to COVID-19 (eg, exposure to someone with a confirmed case of COVID-19), it will be captured in the COVID-19 exposure form, and the participant will continue to follow all remaining study assessments as scheduled. Likewise, participants with a confirmed case of COVID-19 will continue to follow all remaining study assessments as scheduled.

Any confirmed symptomatic COVID-19 infection occurring in participants will be captured as an MAAE along with relevant concomitant medications and details about severity, seriousness, and outcome.

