Confirm participant meets inclusion and exclusion criteria	X									
Physical examination including vital signs ³	X	X			X	X			X	X
Pregnancy testing		X								
Blood for SARS-CoV-2 serology (antinucleocapsid antibody)		X			X	X			X	X
Blood for immune response to vaccination (binding and neutralizing antibody) ⁴		X		X	X	X			X	X
Nasopharyngeal swab sample for SARS-CoV-2 ⁴		X			X	X			X	X ⁵

Visit Number	A.2 Screening ¹	V6		V7	V8	V9			V10	A.2 UNS
Type of Visit	C	C	SC	C	C	C	SFU (eDiary)	SFU (SC)	C	C
Month Timepoint	M0	M0			M1	M3			M6	--
Study Visit Day	D0 ¹	D1 ^{1,9}	D8	D15	D29	D91	Every 2 weeks D36– D162 ²	Every 2 weeks D43–D169	D181	
Window Allowance (Days)	-7	0	+3	±3	-7	±7	±2	±3	±14	--
Days Since Booster Injection		0	7	14	28	90	--		180	--
eDiary activation for recording solicited local and systemic reactogenicity adverse reactions (7 days)		X								
Review of eDiary			X							
Follow-up safety calls ⁶			X					X		
Recording of unsolicited AEs		X	X	X	X					
Recording of MAAEs and concomitant medications relevant to or for the treatment of the MAAE ⁷		X	X	X	X	X	X	X	X	
Recording of SAEs and concomitant medications relevant to or for the treatment of the SAE ⁷		X	X	X	X	X	X	X	X	
Recording of AESI		X	X	X	X	X	X	X	X	
Recording of concomitant medications and non-study vaccinations ⁸		X	X	X	X				X	
Study completion									X	

Abbreviations: AE = adverse event; AESI = adverse event of special interest; C = clinic visit; COVID-19 = coronavirus disease 2019; D = day; eDiary = electronic diary; M = month; MAAE = medically attended adverse event; NP = nasopharyngeal; RT-PCR = reverse transcriptase polymerase chain reaction; SAE = serious adverse event; SARS-CoV-2 = severe acute respiratory syndrome coronavirus 2; SC = safety telephone call; SFU = safety follow-up; UNS = unscheduled visit; V = visit.

Note: In accordance with “FDA Guidance on Conduct of Clinical Trials of Medical Products during COVID-19 Public Health Emergency” ([DHHS 2023](#)), investigators may convert study site visits to telemedicine visits with the approval of the Sponsor.

1. The Screening Visit and Day 1 (vaccination) visit can be combined and occur on the same day.
2. Safety follow-up via eDiary questionnaire will be performed every 2 weeks from Day 36 to Day 162. These study days are relative to Day 1 vaccination. Adverse reactions recorded in the eDiary beyond Day 7 should be reviewed by the study site staff either during the next scheduled telephone call or at the next study site visit.

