With approximately 375 participants exposed to 50 μ g mRNA-1273.214, there is at least 90% probability in this group to observe 1 participant reporting an AE if the true rate of AEs is 1%.

Part H

The target enrollment is approximately 500 participants for 50 μ g mRNA1273.222. Assuming 40% of participants will be excluded from the PPIS-Neg (due to a SARS-CoV-2 infection pre-booster), with approximately 300 participants in 50 μ g mRNA1273.222 and 260 participants in 50 μ g mRNA-1273 (Part F, Cohort 2-50 μ g mRNA-1273) in the PPIS and SARS-CoV-2 negative, there is approximately 60% power to demonstrate the primary immunogenicity objectives with alpha of 0.05 (2-sided) at Day 29. The assumptions are: the true GMR (mRNA-1273.222 second booster vs. 50 μ g mRNA-1273 second booster) against Omicron BA.4/5 is 1.5, GMR (mRNA-1273.222 second booster vs. mRNA-1273 second booster) against ancestral SARS-CoV-2 D614G is 1, the standard deviation of the log-transformed titer is 1.5, and the non-inferiority margin for GMR is 1.5. The true SRR against Omicron BA.4/5 after mRNA-1273.222 as a second booster dose is 95% (same assumption for 50 μ g mRNA-1273), and non-inferiority margin for SRR difference against Omicron BA.4/5 is 5%. The true SRR against ancestral SARS-CoV-2 D614G after mRNA-1273.222 as a second booster dose is 95% (same assumption for 50 μ g mRNA-1273), and the non-inferiority margin for SRR difference against ancestral SARS-CoV-2 D614G is 10%.

With approximately 500 participants exposed to 50 μ g mRNA-1273.222, there is at least 90% probability in this group to observe 1 participant reporting an AE if the true rate of AEs is 1%.

Part J

The sample size for Part J is not driven by statistical assumptions for formal hypothesis testing. The number of proposed participants is considered sufficient to provide a descriptive summary of the safety and immunogenicity of each treatment arm.

The target enrollment is approximately 100 participants who will be randomized in a 1:1 ratio to receive either mRNA-1273.815 (50 μ g) or mRNA-1273.231 (50 μ g).

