5.5. Per-Protocol Immunogenicity SARS-CoV-2 Negative Set (PPIS-Neg)

The PPIS-Neg Set consists of P205 participants who meet all requirements for the PPIS and have no serologic or virologic evidence of SARS-CoV-2 infection at baseline and P201B participants who were in the Per-Protocol Set for Part B.

mRNA-1273-P205 participants

- a) Received the planned dose of study vaccination per schedule
- b) For Parts A.1, A.2, B, C, D, F, G, H: had pre-booster and Day 29 (occurring between 21 and 42 days after vaccination) neutralizing antibody data; for Part J: had pre-booster and Day 15 neutralizing antibody data
 - Part A.1: against B.1.351 variant
 - Part A.2: against B.1.1.529 variant
 - Part B: against ancestral SARS-CoV-2
 - Part C: against B.1.617.2 variant
 - Part D: against B.1.351 variant and B.1.617.2 variant
 - Part F (Cohort 1 and Cohort 2): against B.1.1.529 variant
 - Part G: against B.1.1.529 variant
 - Part H: against BA.4/5 variant
 - Part J: against XBB.1.5 variant

- c) Had no major protocol deviations that impact key or critical data
- d) Had no previous HIV infection
- e) Have no serologic or virologic evidence of SARS-CoV-2 infection at baseline (ie, who are SARS-CoV-2 negative, defined by both negative RT-PCR test for SARS-CoV-2 and negative serology test based on bAb specific to SARS-CoV-2 nucleocapsid)

mRNA-1273-P201B external comparator

Consists of P201B participants after 100 µg primary series who were in Per-Protocol Set for Part B (please refer to P201 SAP version 5.0 Section 5.6 for details).

The PPIS-Neg Set will be used as the primary analysis set for analyses of immunogenicity for Parts A.2, F (Cohort 1), F (Cohort 2), G, and H.

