6.1. General Considerations

Please refer to the protocol for Schedule of Events (SoE).

Continuous variables will be summarized using the following descriptive summary statistics: the number of subjects (n), mean, standard deviation (SD), median, minimum (min), and maximum (max).

Categorical variables will be summarized using counts and percentages.

Baseline value, unless specified otherwise, is defined as the most recent non-missing measurement (scheduled or unscheduled) collected before the dose of IP in this study. Pre-booster and baseline are used interchangeably for the study arms in P205. For immunogenicity tests, the baseline is defined as the most recent non-missing measurement (scheduled or unscheduled) collected before the dose of IP.

For the summary statistics of all numerical variables, unless otherwise specified, the display precision will follow programming standards. Refer to [Appendix A](#) for variable display standards.

When count data are presented, the percentage will be suppressed when the count is zero in order to draw attention to the non-zero counts. “Missing” will be included in count tabulations where specified on the shells to account for dropouts and missing values. The denominator for all percentages will be the number of subjects in the corresponding group, unless otherwise specified.

Pre-booster SARS-CoV-2 status is determined by using virologic and serologic evidence of SARS-CoV-2 infection on or before Day 1 (pre-booster).

Positive SARS-CoV-2 status at pre-booster is defined as a positive RT-PCR test for SARS-CoV-2, and/or a positive serology test based on bAb specific to SARS-CoV-2 nucleocapsid (as measured by Roche Elecsys Anti- SARS-C oV-2 assay) on or before Day 1.

Negative status at pre-booster is defined as a negative RT-PCR test for SARS-CoV-2 and a negative serology test based on bAb specific to SARS-CoV-2 nucleocapsid (as measured by Roche Elecsys Anti- SARS-CoV-2 assay) on or before Day 1.

Study day relative to the injection will be calculated as follows:

- a) study day prior to the injection will be calculated as: date of assessment/event – date of the injection;
- b) study day on or after the date of the injection will be calculated as: date of assessment/event – date of the injection + 1;

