6.4.3. Primary Analysis of Antibody-Mediated Immunogenicity Endpoints

Part A.2

For Part A.2 participants, Day 29 and Day 181 immune response after mRNA-1273.214 (50 µg) as a second booster dose will be compared with their own Day 29 and Day 181 immune response of mRNA-1273.211 (50 µg) received as the first booster dose. GMT ratios will be calculated by back transforming the mean of paired differences of antibody titer data on the logarithmic scale between Day 29 and Day 181 post mRNA-1273.214 and Day 29 and Day 181 of antibody titer data post mRNA-1273.211. CIs for the GMT ratio will be based on t-distribution of the log-transformed values then back transformed to the original scale for presentation. Seroresponse rates at Day 29 and Day 181 post mRNA-1273.214 will be compared with their seroresponse rates at Day 29 and Day 181 post

mRNA-1273.211. The difference in seroresponse rates and its corresponding 95% CI based on adjusted Wald method will be provided.

Part F Cohort 1

Primary analysis set for immunogenicity objectives will be based on PPIS-Neg.

For the primary objective on immune response for a first booster dose of 50 μ g mRNA-1273.529, see [Section 4.2](#). An analysis of covariance (ANCOVA) model will be performed to assess the difference in immune response between mRNA-1273.529 and mRNA-1273 (P201B 50 μ g booster after 100 μ g primary series) as the first booster dose. For immune response against the B.1.1.529 strain, in the ANCOVA model, antibody titers at Day 29 post-booster against the B.1.1.529 strain will be a dependent variable, and a group variable (mRNA-1273.529 and mRNA-1273) will be the fixed effect, adjusting for age groups (< 65 , ≥ 65 years) and pre-booster antibody titer level if applicable; the model may also be adjusted for other characteristics.

The GMT will be estimated by the GLSM from the model and its corresponding 95% will be provided for each group. The GMR (ratio of GMTs) for mRNA-1273.529 with respect to mRNA-1273 will be estimated by the ratio of GLSM from the model and the corresponding 95% CIs will be provided. The 95% CI for GMR will be used to assess the between group difference in immune response against the B.1.1.529 strain for mRNA-1273.529 at Day 29 compared to the mRNA-1273.

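### Part A.2's primary Day 181 titre ratio screens out infection detected before the second booster but not after it, which biases the ratio upward in favour of mRNA-1273.214

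*SAP*

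**What the plan says.** **Contrast.** Under SAP 6.4.3 (Part A.2), participants' responses after mRNA-1273.214 "will be compared with their own Day 29 and Day 181 immune response of mRNA-1273.211". The GMT ratio is the back-transformed mean within-person log difference with a t-based interval. The seroresponse rate (SRR) difference gets an adjusted Wald interval. SAP 3.1 makes both primary endpoints at Day 29 and Day 181. Part A.2 has no hypothesis test, margin, alpha or power statement.

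**Analysis set.** SAP 5.5 says PPIS-Neg "will be used as the primary analysis set for analyses of immunogenicity for Parts A.2, F (Cohort 1"), Part F Cohort 2, G and H. SAP 6.4 and Protocol Table 15 agree. Protocol 8.5.3 instead lists Part A.2 under PPIS. The SAP's introduction says the SAP governs where the two differ.

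**Entry to the set.** Members must "have no serologic or virologic evidence of SARS-CoV-2 infection at baseline". SAP 6.1 adds: "Pre-booster SARS-CoV-2 status is determined by using virologic and serologic evidence of SARS-CoV-2 infection on or before Day 1 (pre-booster"). For immunogenicity tests, "the baseline is defined as the most recent non-missing measurement (scheduled or unscheduled) collected before the dose of IP".

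**After dosing.** SAP 6.1 censors immune-response data at an off-study COVID-19 vaccine and does not mention infection. SAP 6.4.6 permits, without requiring, a sensitivity analysis of the primary immunogenicity endpoints that drops records after infection. Appendix F (changes in version 3.0) gives the reason: natural immunity can also raise titres.

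**The concern.** A within-person ratio is informative only if both members of the pair are handled alike. Here the infection screen falls between the two follow-up periods. It looks back over the mRNA-1273.211 period and removes people with detected infection there. No such rule applies to the mRNA-1273.214 period, so titres raised by infection remain in the numerator only.

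Part A.2 has no concurrent control arm in which the same infections would appear. With no test to fall back on, the estimate and its confidence interval are the whole result. A Day 181 ratio above 1 could then reflect infection as well as the vaccine.

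**Working it through.** **1. Order of events.** A Day 181 titre that reflects mRNA-1273.211 alone must be drawn before mRNA-1273.214 is given. Protocol Table 18, footnote 9, allows Part A.2 Day 1 to coincide with Part A.1 Day 366, so on that schedule the Part A.1 Day 181 sample comes first. The infection screen is applied later, at Part A.2 Day 1.

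**2. Denominator.** Part A.2 has its own Day 1 swab and serology (the Table 18 row beginning "Blood for SARS-CoV-2 serology (antinucleocapsid antibody"). Protocol 7.1.6 describes the tests as complementary, "with the serologic assay detecting previously resolved SARS-CoV-2 infections that may have occurred between visits". With status judged on evidence on or before Day 1, a participant with detected infection during Part A.1 follow-up is not in PPIS-Neg. The remaining Day 181 titres after mRNA-1273.211 come from people with no detected infection.

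**3. Numerator.** Neither SAP 5.5 nor the Part A.2 text of 6.4.3 sets a post-dose infection rule. Protocol 7.1.6 keeps participants with confirmed COVID-19 on the remaining assessments, so their Day 181 titres enter the ratio.

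**4. The pairs exist.** SAP Table 3 shows Day 181 titres against D614G, BA.1 and B.1.351 after both 50 µg mRNA-1273.211 and mRNA-1273.214.

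**5. Size.** The plan gives no figure to reproduce. Let δ be the mean paired log difference without infection, p the share infected between mRNA-1273.214 and Day 181, and f the fold rise in titre from infection. The expected mean becomes δ + p·ln f, and back-transforming gives e^δ × f^p. The ratio is therefore multiplied by f^p. Both p and f are assumptions:

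| p | f = 2 | f = 3 | f = 5 |
|---|---|---|---|
| 10% | 1.07 | 1.12 | 1.17 |
| 25% | 1.19 | 1.32 | 1.50 |
| 40% | 1.32 | 1.55 | 1.90 |

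**6. Effect on the interval.** A simulation (5,000 replicates) took a true ratio of 1, 200 pairs, f = 4, and a paired SD on the natural-log scale from 1.5 down to 0.75. All of these are assumed. The SAP gives an SD of 1.5 for log titre in other parts and none for a paired difference. The 95% interval should lie wholly above 1 in 2.5% of runs. It did so in 10% to 22% at p = 5%, 24% to 62% at p = 10%, and 69% to 99% at p = 20%.

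**7. After the change.** Dropping records after a post-mRNA-1273.214 infection leaves pairs with no detected infection on either side, so the factor is f^0 = 1. Of 200 pairs, 200 × (1 − 0.10) = 180 remain at p = 10%, and 200 × (1 − 0.25) = 150 at p = 25%.

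**The case against.** **The plan already has the remedy.** SAP 6.4.6 covers this endpoint and Appendix F states the mechanism. A reader might infer that the problem was overlooked, and the documents do not support that. What stands is that the analysis is optional and secondary.

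**The set may be PPIS.** If Protocol 8.5.3 governed, infections before mRNA-1273.214 would stay in and the built-in asymmetry would go. Some imbalance could remain: with 5% infected before, 25% after and f = 4, the factor is 4^(0.25 − 0.05) = 1.32, against 4^0.25 = 1.41 under PPIS-Neg. The SAP prevails by its own rule, but a current protocol section contradicts it.

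**Including infection can be a legitimate choice.** One may want the response as it occurs, infection included. That would call for keeping infections on both sides, and PPIS-Neg does not do so.

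**The SAP does not fix p.** A reader might infer 25% from the planned exclusions, because Part H reads "Assuming 40% of participants will be excluded from the PPIS-Neg (due to a SARS-CoV-2 infection pre-booster") and Part G assumes 20%: (0.40 − 0.20)/(1 − 0.20) = 0.25. The Part G figure is not attributed to infection. The Part H paragraph also counts on 260 evaluable in the Part F mRNA-1273 arm, planned at about 375, which is 1 − 260/375 = 30.7% excluded. That would give (0.400 − 0.307)/0.693 = 13%, with factors of 1.10 to 1.24 for f from 2 to 5. Both are planning rates at baseline in other cohorts, not incidence after a second booster. The table above therefore rests on assumed shares.

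**The set is not proven infection-free.** A reader might infer that everyone infected between boosters is removed. Only those with RT-PCR or anti-nucleocapsid evidence are; an undetected infection, or one whose antibody has faded, can remain. Reading baseline as the mRNA-1273.214 Day 1 is natural but is not spelled out for people dosed twice in the study.

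**Conclusion.** The point holds for the Part A.2 primary Day 181 GMT ratio under the governing SAP text. The direction is upward, in favour of mRNA-1273.214, and follows from the one-sided infection rule plus the SAP's own statement that infection raises titres. The size depends on an infection share and a fold rise that the documents do not give.

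Three stronger readings are not supported. Day 29 is not comparably affected, because the window for infection is short. The SRR difference has not been shown to move by a similar amount: primary seroresponse is measured from before dose 1 of the primary series (SAP 6.4.7), so the effect depends on how close Day 181 rates already are to their ceiling, and it is not quantified here. Nor is infection the only obstacle to reading the ratio as relative durability, since dose number and calendar time differ between the two members of each pair and would still do so after the change.

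**What to change.** In SAP 6.4.3 (Part A.2), apply the 6.4.6 exclusion to the Day 181 comparison: drop records after a positive RT-PCR or anti-nucleocapsid test that follows mRNA-1273.214. Make this the primary handling or, at minimum, a mandatory analysis reported beside the all-records result. State that baseline infection status for Part A.2 is taken at the mRNA-1273.214 Day 1. Reconcile Protocol 8.5.3 (PPIS for Part A.2) with Table 15 and SAP 5.5 and 6.4 (PPIS-Neg).

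The cost is SAP and protocol wording and one rerun. The method is already written, and Table 18 already schedules swabs and serology at Days 29, 91 and 181. The price is fewer Day 181 pairs and an estimate that applies to participants who remain uninfected. Because the data are paired, dropping a pair removes the same person from both sides.
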